Title: Neuroplastic Mechanisms Underlying Augmented Neuromuscular Training

NCT#: NCT04069520

Date: 04/01/2024

PROTOCOL TITLE: Neuroplastic Mechanisms Underlying Augmented Neuromuscular Training

PRINCIPAL INVESTIGATOR:

Name: [name]
Department of Orthopedics

[REDACTED]
[REDACTED]

EXTERNAL (NON-EMORY) COLLABORATORS

[name], Associate Professor, Ohio University, Physical Therapy

VERSION: Version 4.0; 04/01/2024

FUNDING SOURCE:

National Institutes of Health

1. Study Summary

Study Title	Neuroplastic Mechanisms Underlying Augmented Neuromuscular Training
Study Design	Randomized Controlled Trial
Primary Objective	To determine the neural mechanisms of acquisition of injury-resistant movement from augmented neuromuscular training
Secondary Objective(s)	To determine the neural mechanisms for injury-resistant movement pattern transfer to VR-simulated sport.
Research Intervention(s)/Interactions	Intervention (Augmented Neuromuscular Training) as described in parent study Real-time Sensorimotor Feedback for Injury Prevention Assessed in Virtual Reality
Study Population	Adolescent Female Athletes
Sample Size	Up to 120 athletes
Study Duration for individual participants	Approximately 6 weeks-4months (includes up to 2 study visits)
Study Specific Abbreviations/ Definitions	Augmented Neuromuscular Training (aNMT)
Funding Source (if any)	National Institutes of Health

2. Objectives

The purpose of this proposal is to determine the neural mechanisms of augmented neuromuscular training (aNMT).

The objective of the current proposal is to utilize our neuroimaging breakthroughs to identify the neural mechanisms responsible for neuromuscular training-induced sensorimotor adaptation and transfer of injury-resistant movement patterns to sport. Our preliminary data indicate that training related neural sensory integration activity supports efficient motor cortex activity which promotes the transfer of injury-resistant movement patterns.^{26,30-34}

3. Background

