Limitations in measuring brain activity associated with the sensorimotor control of dynamic lower extremity movements have been the main barrier to identifying the neural mechanisms underlying the adaptation and transfer of injury-resistant movement patterns. We have overcome this barrier by developing novel neuroimaging paradigms of functional lower extremity movements that engage the fundamental sensorimotor capabilities of knee position and force control underpinning injury-resistant movement control.^{25,29} The objective of the current proposal is to utilize our neuroimaging breakthroughs to identify the neural mechanisms responsible for neuromuscular training-induced sensorimotor adaptation and transfer of injury-resistant movement patterns to sport. Our preliminary data indicate that training related neural sensory integration activity supports efficient motor cortex activity which promotes the transfer of injury-resistant movement patterns.^{26,30-34}

Summary of Prior Work

We have successfully collected data at Cincinnati Children's Hospital Medical Center using our functional knee motor tasks on healthy female participants (Study, Effects of Neuromuscular Training on EEG Adaptations in Young Athletes; PI [name] and Study, Novel Protection against Potential Brain Injury during Competitive Non-helmeted Sport in Females; PI [name]). Our preliminary work demonstrated efficacy in collecting the data while minimizing head motion and establishing reliability across testing sessions. Head motion was limited to .23-.43 mm of absolute motion and .06-.11 mm of relative head motion across all tasks. Intraclass correlation coefficients demonstrated high between session reliability (ICC: .82-.94) for primary motor cortex mean for all tasks ($n = 13$). Participants have reported no problems with the tasks and the majority have returned for subsequent testing.

4. Study Endpoints

The post-training study visit is the study's primary endpoint.

5. Study Intervention/Investigational Agent

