As described in parent study “Real-time Sensorimotor Feedback for Injury Prevention Assessed in Virtual Reality” innovative augmented neuromuscular training (aNMT) techniques will be used to enhance sensorimotor learning and reduce biomechanical risk factors for ACL injury. aNMT integrates biomechanical screening with state-of-the-art augmented reality headsets to display real-time feedback that maps complex biomechanical variables onto simple visual feedback stimuli that participants “control” via their own movements.

6. Procedures Involved

Study Design

Enrolled participants will complete MRI testing pre- and post-aNMT (which is a component of parent study: “Real-time Sensorimotor Feedback for Injury Prevention Assessed in Virtual Reality” and is required to be completed to fully participate in the present study). All MRI scanning will be performed on GE SIGNA™ Premier 3.0 Tesla MR scanners in the EMORY Sports Performance and Research Center (SPARC), located at the Atlanta Falcons’ Flowery Branch NFL headquarters and practice facility. Sedation will not be used for any of the test visits. The entire MRI protocol may include high resolution T1-weighted 3D images, a 61 direction diffusion tensor imaging sequence, resting state fMRI, and task-based fMRI. The task-based fMRI will be focused on motor function, participants will be asked to complete lower extremity movements including knee flexion and extension (see image below) and a combined hip and knee flexion and extension. The MR scan will be completed in 90 minutes or less. Peripheral pulse oximetry and respiration waveforms may also be collected for data analysis in order to minimize the potential confounding effect from the physiological changes. Biomechanics data of the leg segments may be collected using a custom designed MRI safe motion capture system . Reflective markers compatible with MRI system may be attached to the subject’s thighs and shanks using Velcro straps as seen in image below. A practice session of the fMRI paradigms will be completed just prior to scanning to allow the participant to ask any questions and be familiar with the protocol.

Study Procedures

Anthropometrics

Height and weight will be collected. Hand and leg dominance will be asked based on the two questions of, which hand does the participant write with and which foot does the participant use to kick a ball.

Questionnaires

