A series of non-invasive questionnaires pertaining to general health history, physical activity, and knee pain may be administered including a general demographics questionnaire, the International Physical Activity Questionnaire short form (IPAQ_short), and the Movement Imagery Questionnaire-3 (MIQ-3). The MIQ-3 is a 12-item questionnaire that assesses an individual's ability to imagine four movements using: 1) Internal visual imagery 2) External visual imagery and 3) Kinesthetic imagery. The MIQ-3 can quantify motor imagery dominance for the athletes enrolled in the present study.

Subjects may also be asked, "Have you ever been diagnosed with patellofemoral pain." If yes, subjects will also complete the following knee pain questionnaires: Anterior Knee Pain Scale (AKPS), shortened knee pain scale, the Tampa Scale Kinesiophobia (TSK) questionnaire, and the International Knee Documentation Committee (IKDC) scale. If subjects answer no, they will complete the same knee pain questionnaires, but will complete the Tampa Scale Kinesiophobia General (TSK-G; used for pain free controls) instead of the TSK.

All questionnaires may be administered via Redcap surveys during each study visit.

Flanker Test

Participants may also complete the Flanker Test. The flanker test is a non-invasive, 7-minute computer based task that measures response inhibition by assessing visual-motor responsiveness. Specifically, a series of stimuli (arrows) are presented that are congruent (same

direction) or incongruent (different) with a target stimuli (visual) that a participant must respond to (key press) as quickly and accurately as possible (motor response) for testing their visual-motor capability. Including this test will provide an opportunity to gather prospective data regarding participants' visual-motor capability that can be associated with changes in brain activity following augmented neuromuscular training. Specifically, exploratory analyses will use these data as behavioral correlates (or covariates) in the neuroimaging analyses and/or for sub-group analyses based on inter-individual differences in visual-motor capability.

Trail Making Test

Participants may also complete the Trail Making test, which is a computer/tablet based task in which participants connect dots as quickly as they can with minimizing errors. This task provides visual motor capability data to supplement that of the Flanker Test.

MR imaging data Acquisition:

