flexion/extension task and a combined knee and hip flexion/extension movement while keeping the rest of their body still. Peripheral pulse oximetry and respiration waveforms may also be collected for data analysis in order to minimize the potential confounding effect from the physiological changes. A practice session of the fMRI paradigms will be completed just prior to scanning to allow the participant to ask any questions and be familiar with the protocol. Each MR scan will be completed in 90 minutes or less. If participants withdraw from the parent study, "Real-time Sensorimotor Feedback for Injury Prevention Assessed in Virtual Reality" or do not complete the aNMT program, they may not be eligible to complete the post-training MRI session for this study.

In the event that technical issues arise during an MRI and the entire scan session is not able to be completed, a participant may be asked to return to complete the session once the technical issue has been resolved. In this event, the participant will be compensated accordingly for both visits. Every effort will be made to re-schedule the appointment; however, there may not be an option to re-schedule due to time constrictions or participant schedule conflicts. If this occurs then the tests not administered due to technical issues will be considered as lost for analysis.

If an enrolled participant sustains a lower extremity or concussion injury, she may repeat all tests performed at the pre-training appointment as well as the opportunity to participate in longitudinal follow-up brain fMRIs and joint specific structural imaging. The brain fMRI paradigms will be identical to the current protocol. All movements will be monitored for patient pain or discomfort and not completed if patient reports unacceptable pain. Additionally, to further evaluate neuroplasticity associated with injury, anatomical/structural MRI sequence may be completed during study visits. The structural MRI may include relevant sequences such as coronal proton-density imaging, T2 mapping, T1 weighted, T1 rho. The structural MRIs may be repeated or captured simultaneously on the non-injured limb for comparative purposes regarding the time course of healing. The additional structural MRI sequences would not last more ~45 minutes.

7. Data and Specimen Banking

N/A

8. Sharing of Results with Participants

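### The study is labelled a randomised controlled trial of mechanisms from aNMT, but the plan states no comparator or between-arm contrast and restricts the second scan to those who complete aNMT

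*Protocol*

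**What the plan says.** The Protocol's section 1 (Study Summary) gives the design as "Randomized Controlled Trial" and the primary objective as "To determine the neural mechanisms of acquisition of injury-resistant movement from augmented neuromuscular training". The only intervention listed is aNMT, by reference to the parent study. The sample is up to 120 athletes, with no split by arm. Section 4 (Study Endpoints) says "The post-training study visit is the study's primary endpoint", which names a visit and not a measure or a contrast.

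Section 6 (Study Design) says "Enrolled participants will complete MRI testing pre- and post-aNMT" and that aNMT "is required to be completed to fully participate in the present study". The Compensation text, in sections 13 and 17, makes the second session conditional on finishing the aNMT programme. The Combined protocol and SAP, section (4), places the same completion requirement on the neuromuscular training.

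Two other places deal with the second scan. Section 6 (MR imaging data Acquisition) says that participants who withdraw from the parent study or "do not complete the aNMT program, they may not be eligible to complete the post-training MRI session for this study". Section 14 (Withdrawal of Participants) says that leaving the parent study before the post-training visit ends eligibility automatically. It also allows data collected before withdrawal to be used.

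**The concern.** A design label is a claim about what the comparison can support. A randomised controlled trial attributes a difference to the intervention because a concurrent group, formed by chance, goes through the same interval without it. The objective, mechanisms arising from aNMT, needs that attribution. The scanning rules do not provide for it. They describe one sequence (scan, train, scan) and admit to the second scan only those who finish the training.

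Two things are at stake. The first is attribution: without a comparator, a change in brain activity between two scans could come from the training or from the passage of time. The second is selection. If the parent study does have randomised arms, a rule tied to completing aNMT would remove non-completers from one arm and, read literally, leave the other arm with no data at the primary endpoint.

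**Working it through.** **1. Search for a comparator or contrast.** No section of either document states an allocation ratio, a randomisation method or a comparator arm. The nearest wording is:
- Protocol section 18 (Data Analysis): software, resting-state connectivity and joint-angle processing, with no contrast.
- Combined protocol and SAP section (9): an optional voxel-based DTI analysis that could look at group differences or change over time, with no groups named.
- Protocol section 6 (Flanker Test): exploratory "sub-group analyses based on inter-individual differences in visual-motor capability". These groups are defined by capability, not by allocation.
- Protocol section 6 (Questionnaires): pain-free controls, meaning respondents to one form of a questionnaire, not a trial arm.

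**2. Second-scan rules side by side.**

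| Place | Event addressed | Force |
|---|---|---|
| Protocol 6, Study Design | completing aNMT | required for full participation |
| Protocol 13 and 17, Compensation | completing aNMT | mandatory for session two |
| Combined protocol and SAP (4) | completing neuromuscular training | required for full participation |
| Protocol 6, MR imaging data Acquisition | non-completion; parent-study withdrawal | discretionary |
| Protocol 14, Withdrawal | parent-study withdrawal | automatic; silent on non-completion |

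The conflicts are therefore between the MRI procedures text and the Compensation text on non-completion, and between the MRI procedures text and section 14 on withdrawal.

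**3. What the plan as written estimates.** Let T be the effect of training and D the change over the interval from everything else (repeat scanning, practice of the task, season, maturation). In completers, the expected second-minus-first difference is T + D. One quantity is observed and two are unknown, so T is not identified. With a randomised comparator scanned at the same times and sharing D, the between-arm difference is (T + D) − D = T. That holds only if the people scanned twice are still comparable between arms, which a completion rule in one arm undermines.

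**4. Whether size can be computed.** The documents give no drift, attrition, arm sizes, alpha, power or scalar test, so there is no stated figure to reproduce, and the 120 has no derivation. For illustration only, assume a two-sided 0.05 paired test on one scalar measure, N = 120, T = 0 and between-session correlation r. The SD of change is sqrt(2(1 − r)): 1.00, 0.60 and 0.346 for r = .5, .82 and .94. The noncentrality is D × sqrt(120) / sqrt(2(1 − r)).
- D = 0.02 SD: rejection rates 5.5%, 6.5% and 9.6%.
- D = 0.10 SD: rejection rates 19%, 44% and 88%.

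The values .82 and .94 are the ends of the range in section 3: "Intraclass correlation coefficients demonstrated high between session reliability (ICC: .82-.94) for primary motor cortex mean for all tasks". They come from 13 people and one region; r = .5 and both drifts are assumed. The spread from negligible to large shows that the arithmetic cannot settle the size, and the point does not rest on it.

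**The case against.** The strongest reply is that the arms belong to the parent study. The Protocol defers to it for the intervention, so a randomised comparator may well exist there. This stands as a limit on the point: a reader might infer that there is no control arm, and the documents do not support that. They show only that neither of them names one. The parent protocol would not by itself remove the completion conditions written here, nor supply this study's imaging contrast.

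A second reply is that a within-person contrast is plainly intended, since section 6 speaks of changes in brain activity after aNMT. That is a fair reading. It favours correcting the label rather than keeping it.

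A third is that the reported reliability is high. But the documents do not say which form of ICC was used or how far apart the sessions were, and a consistency-type ICC is unaffected by a shift in the mean.

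A stronger reading is tempting: that the documents contradict themselves on whether completing aNMT or parent-study enrolment alone qualifies someone for the second scan. They do not. Protocol section 10 sets entry criteria. Protocol section 9 and Combined protocol and SAP section (5) say when visit 2 takes place. Section 14 makes continued enrolment necessary, not sufficient. All of these are compatible with a completion requirement. The payment section (17) of the Combined protocol and SAP, written for another site, lacks the completion sentence, but silence there is not permission.

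**Conclusion.** The point holds and should be fixed. The label and objective claim a controlled comparison that the stated rules do not deliver. As written, the second-scan data come from aNMT completers, and the result is a change over 6 weeks to 4 months that cannot be attributed to training. The discretionary wording in the MRI procedures text is a separate and smaller inconsistency. It affects only non-completers and those who leave the parent study, whose number is unknown.

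No numerical size can be given. Confidence is medium, because the parent protocol may define randomised arms. If it does, the defect is a missing contrast and a selective scan rule; if it does not, the defect is the label and the breadth of the claim.

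**What to change.** First reconcile the MRI procedures text in Protocol section 6 with the Study Design and Compensation text on non-completion, and with section 14 on parent-study withdrawal, giving each event its own rule. Then choose one of two routes.

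**(a) The imaging cohort includes randomised arms of the parent study.** Name the comparator. State the second-scan rule so that it applies to every arm and does not select on completing aNMT. Make the primary analysis a between-arm comparison, as randomised, of a named imaging measure adjusted for the pre-training scan. Report by arm how many lack a second scan, with their first-scan values. That reporting shows the selection but does not remove it, so the scan rule matters more.

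The cost is precision, and second scans not taken cannot be recovered. Assuming 60 per arm, two-sided 0.05 and 80% power (multiplier 1.96 + 0.84 = 2.80), detectable differences in SD units at r = .5, .82 and .94 are:
- baseline-adjusted, 2.80 × sqrt(2/60) × sqrt(1 − r²): 0.44, 0.29, 0.17;
- comparison of change, 2.80 × sqrt(2/60) × sqrt(2(1 − r)): 0.51, 0.31, 0.18;
- one-group paired test of 120, 2.80 × sqrt(2(1 − r)) / sqrt(120): 0.26, 0.15, 0.09.

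At the reported ICCs the two between-arm models differ little.

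**(b) There is no randomised comparator.** Replace the design label in the Study Summary with single-group pre/post, and limit the conclusion to change over time in those scanned twice. This is a wording change, at the price of a narrower claim.

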**(1) ABSTRACT:**

Anterior cruciate ligament (ACL) injury is a common activity-related knee injury with a substantial negative impact on individuals and society. Annual direct costs exceed \$13 billion, and the long-term indirect costs far exceed that figure, as ACL injury is also linked to accelerated development of disabling osteoarthritis within a few years after injury. The National Public Health Agenda for Osteoarthritis recommends expanding and refining evidence-based ACL injury prevention to reduce this burden. We have identified modifiable risk factors that predict ACL injury in young female athletes. Our neuromuscular training targets those factors and shows statistical efficacy in high-risk athletes, but meaningful transfer of low-risk mechanics to the field of play has been limited, as current approaches are not yet decreasing national ACL injury rates in young female athletes. The key gap is how to target mechanisms that allow transfer of risk-reducing motor control strategies from the intervention to the athletic field. The mechanisms that ultimately make such transfer possible are neural, but thus far injury prevention training focusing on neuromuscular control has not utilized neural outcomes. Our published and new preliminary data on neuroplasticity related to injury and neuromuscular training demonstrate our proficiency to capture these neural outcomes and future capability to target these neural mechanisms to improve the rate of motor transfer. The data support this proposal's central hypothesis that increased sensory, visual and motor planning activity to improve motor cortex efficiency is the neural mechanism of adaptation transfer to realistic scenarios. The ability to target the neural mechanisms to increase risk-reducing motor transfer from the clinic to the world could revolutionize ACL injury prevention. The transformative, positive impact of such innovative strategies will enhance the delivery of biofeedback to optimize training and increase the potential for sport transfer. This contribution will be significant for ACL injury prevention and associated long-term sequelae in young females. This unique opportunity to enhance ACL injury prevention by targeting neural mechanisms of neuromuscular adaptation and transfer will reduce the incidence of injuries that cause costly and long-term disabling osteoarthritis.

**(2) PURPOSE:**

The purpose of this proposal is to determine the neural mechanisms of augmented neuromuscular training.

**(3) BACKGROUND:**

Anterior cruciate ligament (ACL) injury is a common and debilitating knee injury affecting over 350,000 children or young adults each year, drastically reducing their chances for an active and healthy life. ACL injury has a substantial negative impact on individuals and society including

direct costs up to \$13 billion annually. Long-term indirect costs far exceed that amount, as ACL injury is linked to accelerated development of disabling osteoarthritis within a few years after injury. The onset of osteoarthritis after ACL injury, combined with a 1 in 4 risk of a subsequent ACL injury, has led the National Public Health Agenda for Osteoarthritis to strongly recommend expansion and refinement of injury prevention strategies. However, the current standard of care for ACL injury prevention, has not decelerated the trajectory of increased non-contact ACL injury rates in susceptible female athletes. Despite extensive efforts, the efficacy of neuromuscular training has not advanced with ~100 patients still requiring treatment to prevent a single ACL injury. Current ACL injury prevention programs can improve isolated knee joint injury risk mechanics (knee abduction motion & loading) during standard testing in the lab, but may be inadequate for the transfer of global injury-resistant movement patterns during demanding functional tasks, limiting translation to sport. Limited transfer of injury-resistant movement patterns likely explains how motor coordination related non-contact ACL injuries still occur despite current best-practice interventions. If injury prevention programs fail to induce adaptation and transfer to sport scenarios, injury risk will not be mitigated no matter how well executed the intervention or compliant the participants. A missing link for improving efficacy is a comprehensive understanding of the neural mechanisms by which the nervous system adapts and transfers injury-resistant movement patterns to new environments (i.e., from the intervention to sport).

Limitations in measuring brain activity associated with the sensorimotor control of dynamic lower extremity movements have been the main barrier to identifying the neural mechanisms underlying the adaptation and transfer of injury-resistant movement patterns. We have overcome this barrier by developing novel neuroimaging paradigms of functional lower extremity movements that engage the fundamental sensorimotor capabilities of knee position and force control underpinning injury-resistant movement control. The objective of the current proposal is to utilize our neuroimaging breakthroughs to identify the neural mechanisms responsible for neuromuscular training-induced sensorimotor adaptation and transfer of injury-resistant movement patterns to sport. Our preliminary data indicate that training related neural sensory integration activity supports efficient motor cortex activity which promotes the transfer of injury-resistant movement patterns.

